2.3. Visit Windows

As subjects do not always adhere to the protocol visit schedule, the following rules are applied to assign actual visits to protocol visits. Listed below are the visit windows and the target days for each visit. The reference day is Study Day 1 (which is the first day that any study drug was taken in the induction phase for subjects who enter the study at the induction phase, and the first day any study drug was taken in the optimization/maintenance phase for responders from induction phase and subjects directly entering the optimization/maintenance phase of this study).

If a subject has 2 or more scheduled or unscheduled visits in one visit window, the visit closest to the target day will be used as the protocol visit for that visit window. If 2 actual visits are equidistant from the target day within a visit window, the later visit is used. If a visit window has no scheduled visits but does have unscheduled visits, then the unscheduled visit closest to the scheduled visit will be used.

All assignments will be made in chronological order. Once a visit is assigned to a visit window, it will no longer be used for a later time point except for the end point.

Listed below are the visit windows and the target days (if applicable) for each visit defined in the protocol for all phases (Table 1).

Table 1: Analysis Visits

Parameter	Analysis Phase	Scheduled Day ^a	Time Interval (label on output)	Time Interval ^a (Day)	Target Time Point ^a (Day)
Montgomery-Asberg Depression Rating Scale (MADRS)	IND	1	Baseline	≤ 1	1
		8	Day 8 (IND)	2 - 11	8
		15	Day 15 (IND)	12 - 18	15
		22	Day 22 (IND)	19 - 24	22
		28	Day 28 (IND)	25 to end of IND	28
		IND final visit	End Point (IND)	2 to end of IND	
	OP/MA i=1,2,3,...	1	Baseline (OP/MA)	≤ 1	1
		15	Week 3 (OP/MA)	2 - 32	15
		50	Week 8 (OP/MA)	33 - 64	50
		50 + i*28	Week (8 + i*4) (OP/MA)	37 + i*28 to 64 + i*28	50 + i*28
OP/MA final visit		End Point (OP/MA)	2 to end of OP/MA		
CGI-S	IND	1	Baseline	≤ 1	1
		4	Day 4 (IND)	2 - 6	4
		8	Day 8 (IND)	7 - 9	8
		11	Day 11 (IND)	10 - 13	11
		15	Day 15 (IND)	14 - 18	15

Table 1: Analysis Visits

Parameter	Analysis Phase	Scheduled Day ^a	Time Interval (label on output)	Time Interval ^a (Day)	Target Time Point ^a (Day)
		22	Day 22 (IND)	19 - 24	22
		28	Day 28 (IND)	25 to end of IND	28
		IND final visit	End Point (IND)	2 to end of IND	
	OP/MA i=1,2,3,...	1	Baseline (OP/MA)	≤ 1	1
		8	Week 2 (OP/MA)	2 - 11	8
		15	Week 3 (OP/MA)	12 - 18	15
		22	Week 4 (OP/MA)	19 - 29	22
		22 + i*14	Week (4 + i*2) (OP/MA)	16 + i*14 to 29 + i*14	22 + i*14
OP/MA final visit	End Point (OP/MA)	2 to end of OP/MA			
Patient Health Questionnaire – 9 item (PHQ-9), EuroQol Group; 5 dimension; 5 level (EQ-5D-5L), Quality of Life in Depression Scale (QLDS)	IND	1	Baseline	≤ 1	1
		15	Day 15 (IND)	2 - 21	15
		28	Day 28 (IND)	22 to end of IND	28
	IND final visit	End Point (IND)	2 to end of IND		
	OP/MA i=1,2,3,...	1	Baseline (OP/MA)	≤ 1	1
		15	Week 3 (OP/MA)	2 - 32	15
		50	Week 8 (OP/MA)	33 - 64	50
		50 + i*28	Week (8 + i*4) (OP/MA)	37 + i*28 to 64 + i*28	50 + i*28
OP/MA final visit	End Point (OP/MA)	2 to end of OP/MA			
Sheehan Disability Scale (SDS)	IND	1	Baseline	≤ 1	1
		28	Day 28 (IND)	2 to end of IND	28
		IND final visit	End Point (IND)	2 to end of IND	
	OP/MA i=1,2,3,...	1	Baseline (OP/MA)	≤ 1	1
		15	Week 3 (OP/MA)	2 - 32	15
		50	Week 8 (OP/MA)	33 - 64	50
		50 + i*28	Week (8 + i*4) (OP/MA)	37 + i*28 to 64 + i*28	50 + i*28
	OP/MA final visit	End Point (OP/MA)	2 to end of OP/MA		
Treatment Satisfaction Questionnaire for Medication (TSQM-9)	IND	1	Baseline	≤ 1	1
		28	Day 28 (IND)	2 to end of IND	28
		IND final visit	End Point (IND)	2 to end of IND	
	OP/MA i=1,2,3,...	1	Baseline (OP/MA)	≤ 1	1
		50	Week 8 (OP/MA)	2 - 64	50
		50 + i*28	Week (8 + i*4) (OP/MA)	37 + i*28 to 64 + i*28	50 + i*28
OP/MA final visit	End Point (OP/MA)	2 to end of OP/MA			
	IND	28	Day 28 (IND)	1 to end of IND	28

Table 1: Analysis Visits

Parameter	Analysis Phase	Scheduled Day ^a	Time Interval (label on output)	Time Interval ^a (Day)	Target Time Point ^a (Day)
Patient Stated-choice Preference	OP/MA	22	Week 4 (OP/MA)	1 to end of OP/MA	22
Nasal exam	IND	1	Baseline	≤ 1	1
		28	Day 28 (IND)	2 to end of IND	28
		IND final visit	End Point (IND)	2 to end of IND	
Vital Signs: Temperature (TEMP) (IND [predose], OP/MA [predose]), Blood Pressure (BP) ^b , Hear Rate (HR), Respiratory (RESP) (IND [predose, 40M, 1H, 1H30M], OP/MA [predose, 40M, 1H])	IND	1	Baseline	≤ 1 / predose	1
			Day 1 (IND): 40M		
			Day 1 (IND): 1H		
			Day 1 (IND): 1H30M		
		4	Day 4 (IND): Predose	2 - 6	4
			Day 4 (IND): 40M		
			Day 4 (IND): 1H		
			Day 4 (IND): 1H30M		
		8	Day 8 (IND): Predose	7 - 9	8
			Day 8 (IND): 40M		
			Day 8 (IND): 1H		
			Day 8 (IND): 1H30M		
		11	Day 11 (IND): Predose	10 - 13	11
			Day 11 (IND): 40M		
			Day 11 (IND): 1H		
			Day 11 (IND): 1H30M		
		15	Day 15 (IND): Predose	14 - 16	15
			Day 15 (IND): 40M		
			Day 15 (IND): 1H		
			Day 15 (IND): 1H30M		
		18	Day 18 (IND): Predose	17 - 20	18
			Day 18 (IND): 40M		
			Day 18 (IND): 1H		
			Day 18 (IND): 1H30M		
		22	Day 22 (IND): Predose	21 - 23	22
			Day 22 (IND): 40M		
			Day 22 (IND): 1H		
			Day 22 (IND): 1H30M		
25	Day 25 (IND): Predose	24 to end of IND	25		
	Day 25 (IND): 40M				
	Day 25 (IND): 1H				
	Day 25 (IND): 1H30M				
IND final visit	IND final visit	End Point (IND)	Day 1 (IND): 40M to end of IND		

Table 1: Analysis Visits

Parameter	Analysis Phase	Scheduled Day ^a	Time Interval (label on output)	Time Interval ^a (Day)	Target Time Point ^a (Day)
	OP/MA i=1,2,3,...	1	Baseline (OP/MA)	≤ 1	1
			Week 1 (OP/MA): 40M		
			Week 1 (OP/MA): 1H		
		8	Week 2 (OP/MA): Predose	2 - 11	8
			Week 2 (OP/MA): 40M		
			Week 2 (OP/MA): 1H		
		15	Week 3 (OP/MA): Predose	12 - 18	15
			Week 3 (OP/MA): 40M		
			Week 3 (OP/MA): 1H		
		22	Week 4 (OP/MA): Predose	19 - 25	22
			Week 4 (OP/MA): 40M		
			Week 4 (OP/MA): 1H		
		22 + i*7	Week (4 + i*1) (OP/MA): Predose	19 + i*7 to 25 + i*7	22 + i*7
Week (4 + i*1) (OP/MA): 40M					
Week (4 + i*1) (OP/MA): 1H					
OP/MA final visit	End Point (OP/MA)	Week 1: 40M to end of OP/MA			
Weight and body mass index (BMI), Hematology and Chemistry, Urinalysis	IND	1	Baseline	≤ 1	1
		28	Day 28 (IND)	2 to end of IND	28
		IND final visit	End Point (IND)	2 to end of IND	
	OP/MA i=1,2,3,...	1	Baseline (OP/MA)	≤ 1	1
		106	Week 16 (OP/MA)	2 - 148	106
		106 + i*84	Week (16 + i*12) (OP/MA)	65 + i*84 to 148 + i*84	106 + i*84
		OP/MA final visit	End Point (OP/MA)	2 to end of OP/MA	
Electrocardiogram (ECG)	IND	1	Baseline	≤ 1 / predose	1
			Day 1 (IND): 1H		
		15	Day 15 (IND): 1H	2 - 20	15
		25	Day 25 (IND): 1H	21 to end of IND	25
	IND final visit	End Point (IND)	Day 1 (IND): 1H to end of IND		
	OP/MA i=1,2,3,...	1	Baseline (OP/MA)	≤ 1	1
			Week 1 (OP/MA): 1H		
		50	Week 8 (OP/MA): 1H	2 - 64	50
50 + i*28		Week (8 + i*4) (OP/MA): 1H	37 + i*28 to 64 + i*28	50 + i*28	

Table 1: Analysis Visits

Parameter	Analysis Phase	Scheduled Day ^a	Time Interval (label on output)	Time Interval ^a (Day)	Target Time Point ^a (Day)	
		OP/MA final visit	End Point (OP/MA)	Week 1: 1H to end of OP/MA		
Columbia-Suicide Severity Rating Scale(C-SSRS)	IND	1	Baseline	≤ 1	1	
		4	Day 4 (IND)	2 - 6	4	
		8	Day 8 (IND)	7 - 9	8	
		11	Day 11 (IND)	10 - 13	11	
		15	Day 15 (IND)	14 - 16	15	
		18	Day 18 (IND)	17 - 20	18	
		22	Day 22 (IND)	21 - 23	22	
		25	Day 25 (IND)	24 - 26	25	
		28	Day 28 (IND)	27 to end of IND	28	
	IND final visit	End Point (IND)	2 to end of IND			
	OP/MA i=1,2,3,...	1	Baseline (OP/MA)	≤ 1	1	
		8	Week 2 (OP/MA)	2 - 11	8	
		15	Week 3 (OP/MA)	12 - 18	15	
		22	Week 4 (OP/MA)	19 - 29	22	
		22 + i*14	Week (4 + i*2) (OP/MA)	16 + i*14 to 29 + i*14	22 + i*14	
		OP/MA final visit	End Point (OP/MA)	2 to end of OP/MA		
	MOAA/S ^c (IND and OP/MA [predose and every 15 minutes to 1H]), CGADR ^d (IND and OP/MA [30M; if not “Yes”, repeat every 15 minutes until “Yes”])	IND	1	Day 1 (IND)	≤ 1	1
			4	Day 4 (IND)	2 - 6	4
8			Day 8 (IND)	7 - 9	8	
11			Day 11 (IND)	10 - 13	11	
15			Day 15 (IND)	14 - 16	15	
18			Day 18 (IND)	17 - 20	18	
22			Day 22 (IND)	21 - 23	22	
25			Day 25 (IND)	24 to end of IND	25	
IND final visit			End Point (IND)	2 to end of IND		
OP/MA i=1,2,3,...		1	Week 1 (OP/MA)	≤ 1	1	
		8	Week 2 (OP/MA)	2 - 11	8	
		15	Week 3 (OP/MA)	12 - 18	15	
		22	Week 4 (OP/MA)	19 - 25	22	
		22 + i*7	Week (4 + i*1) (OP/MA)	19 + i*7 to 25 + i*7	22 + i*7	
		OP/MA final visit	End Point (OP/MA)	2 to end of OP/MA		
Pulse Oximetry ^e (IND [predose and every 15 minutes to 1H]),		IND	1	Baseline	≤ 1	1
			4	Day 4 (IND)	2 - 6	4
			8	Day 8 (IND)	7 - 9	8

Table 1: Analysis Visits

Parameter	Analysis Phase	Scheduled Day ^a	Time Interval (label on output)	Time Interval ^a (Day)	Target Time Point ^a (Day)
OP/MA [predose, 30M, 1H])		11	Day 11 (IND)	10 - 13	11
		15	Day 15 (IND)	14 - 16	15
		18	Day 18 (IND)	17 - 20	18
		22	Day 22 (IND)	21 - 23	22
		25	Day 25 (IND)	24 to end of IND	25
		IND final visit	End Point (IND)	2 to end of IND	
	OP/MA i=1,2,3,...	1	Week 1 (OP/MA)	≤ 1	1
		8	Week 2 (OP/MA)	2 - 11	8
		15	Week 3 (OP/MA)	12 - 18	15
		22	Week 4 (OP/MA)	19 - 25	22
		22 + i*7	Week (4 + i*1) (OP/MA)	19 + i*7 to 25 + i*7	22 + i*7
OP/MA final visit	End Point (OP/MA)	2 to end of OP/MA			
Healthcare Resource Use Questionnaire (HRUQ)	OP/MA i=1,2,3,...	1	Week 1 (OP/MA)	≤ 1	1
		22	Week 4 (OP/MA)	2 - 36	22
		22 + i*28	Week (4 + i*4) (OP/MA)	9 + i*28 to 36 + i*28	22 + i*28
	OP/MA final visit	End Point (OP/MA)	2 to end of OP/MA		
PWC	OP/MA	End Point (OP/MA)	End Point (OP/MA)	1 to end of OP/MA	
	FU	7	Week 1 (F/U)	1 to 10	7
		14	Week 2 (F/U)	11 to 17	14
		21	Week 3 (F/U)	18 to 24	21
		28	Week 4 (F/U)	25 to end of F/U	28
F/U final visit	End Point (F/U)	1 to end of F/U			

^a For IND phase, time interval is relative to the first day of the induction phase.

For OP/MA phase, time interval is relative to the first day of the optimization/maintenance phase.

^b During the IND and OP/MA phase, at 1.5 hours postdose if the systolic blood pressure (SBP) is ≥ 160 and/or the diastolic blood pressure (DBP) is ≥ 100 , blood pressure monitoring should continue every 30 minutes until the blood pressure if SBP < 160 and DBP < 100 , or investigator's clinical judgment the subject it is clinically stable and can be discharged from the study site or the subject is referred for appropriate medical care if clinically indicated. if the blood pressure remains ≥ 180 mmHg SBP and/or ≥ 110 mmHg DBP, 2 hours after dosing, the subject should be referred for immediate medical treatment.

^c If the MOAA/S score is ≤ 3 at any time during the 1 hour postdose interval, the MOAA/S will be performed every 5 minutes until a score of 4 is reached (at which point a frequency of every 15 minutes can be resumed until $t=+1$ hours post dose)

^d If the response is "No", the assessment will be repeated every 15 minutes until a "Yes" response is achieved or until the subject is referred for appropriate medical care if clinically indicated. On all intranasal treatment session days, subjects must remain at the clinical site until study procedures have been completed and the subject is ready for discharge.

^e If pulse oximetry is $< 93\%$ at any time during the 1 hour postdose interval, pulse oximetry will be recorded every 5 minutes until levels return to $\geq 93\%$ or until the subject is referred for appropriate medical care, if clinically indicated

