Concomitant therapy	Ongoing											
Adverse events	Ongoing											

Footnotes:

Abbreviations: CGADR = Clinical Global Assessment of Discharge Readiness; CGI-S = Clinical Global Impression - Severity; C-SSRS = Columbia Suicide Severity Rating Scale; EQ-5D-5L = European Quality of Life (EuroQol) Group, 5-Dimension, 5-Level; EW = Early Withdrawal; 7-item; HbA1c = Hemoglobin A1c; HRUQ = Healthcare Resource Use Questionnaire; HVLTR-R = Hopkins Verbal Learning Test - Revised; MADRS = Montgomery-Asberg Depression Rating Scale; MOAA/S = Modified Observer's Assessment of Alertness/Sedation; PHQ-9 = Patient Health Questionnaire, 9-item; SDS = Sheehan Disability Scale; QLDS=Quality of Life in Depression Scale

Note: On intranasal dosing days, time = 0 is defined as the time of the first intranasal spray. Therefore, “postdose” time points are referenced from this.

- a) Visit window: ±3 days. Clinic visits will be conducted for all intranasal treatment sessions; a remote visit (ie, telephone contact) will be conducted for all other visits with a scheduled study procedure. Due to the variable clinic visit frequency, following Visit 2.4, visit numbers will continue sequentially (eg, 2.5, 2.6, etc) until the subject completes the phase. The frequency of study procedures following Week 4 to the end of the phase is provided within the respective column (ie, every week, 2 weeks, 4 weeks, 8 weeks, 12, and 24 weeks).
- b) The Day 28 visit of 54135419TRD3008 (Visit 1.9) is expected to coincide with Visit 2.1. Results for all predose assessments performed on Day 28 of the induction phase of 54135419TRD3008 (ie, Visit 1.9) will not be repeated as part of Visit 2.1.

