9.2. Safety Evaluations

Details regarding the IDMC are provided in Section 11.7.

Any clinically relevant changes occurring during the study must be recorded on the Adverse Event section of the CRF.

Any clinically significant abnormalities persisting at the end of the study/early withdrawal will be followed by the investigator until resolution or until a clinically stable condition is reached.

The study will include the following evaluations of safety and tolerability according to the time points provided in the Time and Events Schedules.

There may be instances where a subject has started a scheduled clinic visit in which an intranasal treatment session is planned, but due to predose vital sign measurements (eg, blood pressure value), a decision has been made to postpone/delay the intranasal treatment session within the visit window permitted per protocol. In such cases, all time points (including predose) of the following assessments must be repeated on the actual intranasal treatment session day: vital sign (ie, blood pressure, pulse, respiratory rate, and temperature), 12-lead ECG, C-SSRS (since last visit), MOAA/S, and pulse oximetry.

Adverse Events

Adverse events will be reported by the subject (or, when appropriate, by a caregiver, surrogate, or the subject's legally acceptable representative) for the duration of the study. Adverse events will be followed by the investigator as specified in Section 12, Adverse Event Reporting.

Treatment emergent AEs of special interest will be examined separately (please refer to Section 3.2.5 and Section 11.3).

Clinical Laboratory Tests

Blood samples for serum chemistry and hematology and urine samples for urinalysis will be collected. The investigator must review the laboratory results, document this review, and record any clinically relevant changes occurring during the study in the adverse event section of the CRF. The laboratory reports must be filed with the source documents.

The use of local laboratories is allowed in cases where initiation of treatment or safety follow-up is time-critical and the central laboratory results are not expected to be available before the need to begin dosing or if actions need to be taken for safety reasons.

The following tests will be performed by the central laboratory, unless noted otherwise:

- **Hematology panel:**

- | | |
|------------------------|--|
| - hemoglobin | - white blood cell count with differential |
| - hematocrit | - platelet count |

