The C-SSRS is a measure of the spectrum of suicidal ideation and behavior that was developed in the National Institute of Mental Health Treatment of Adolescent Suicide Attempters Study to assess severity and track suicidal events through any treatment.⁵⁸ It is a clinical interview providing a summary of both suicidal ideation and behavior that can be administered during any evaluation or risk assessment to identify the level and type of suicidality present. The C-SSRS can also be used during treatment to monitor for clinical worsening.

The C-SSRS assessments in this study will use the Since Last Visit version, which will assess suicidal ideation and behavior since the subject's last visit.

Modified Observer's Assessment of Alertness/Sedation (MOAA/S)

The MOAA/S will be used to measure treatment-emergent sedation, with correlation to levels of sedation defined by the American Society of Anesthesiologists (ASA) continuum.

The MOAA/S scores range from 0=no response to painful stimulus (corresponds to ASA continuum for general anesthesia) to 5=readily responds to name spoken in normal tone (awake; corresponds to ASA continuum for minimal sedation).

On specified days in the T&E, the MOAA/S will be performed every 15 minutes from predose to $t=+1$ hours postdose.

- If the score is ≤ 3 at any time during the 1 hour postdose interval, the MOAA/S will be performed every 5 minutes until a score of 4 is reached (at which point a frequency of every 15 minutes can be resumed until $t=+1$ hours post dose).
- If a subject does not have a score of at least 5 at $t=+1$ hours postdose, they should continue to be monitored. For subjects with a score of 4, the assessment should be repeated every 15 minutes. And for subjects with a score of ≤ 3 , the assessment should be repeated every 5 minutes until the score returns to 5 or the subject is referred for appropriate medical care, if clinically indicated.

Clinical Global Assessment of Discharge Readiness (CGADR)

The CGADR will be used to measure the subject's current clinical status and is the clinician's assessment of the readiness to be discharged from the study site.

The clinician will answer “Yes” or “No” to the question “*Is the subject considered ready to be discharged based on their overall clinical status (eg, sedation, blood pressure, and other adverse events)?*”

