6.6. Other Safety Parameters

6.6.1. Columbia-Suicide Severity Rating Scale (C-SSRS)

The C-SSRS⁷ is a low-burden measure of the spectrum of suicidal ideation and behavior that was developed in the National Institute of Mental Health Treatment of Adolescent Suicide Attempters Study to assess severity and track suicidal events through any treatment. It is a semi structured clinician-administered questionnaire designed to solicit the occurrence, severity, and frequency of suicide-related ideation and behaviors during the assessment period. Using the C-SSRS, potentially suicide-related events will be categorized using the following scores:

Suicidal Ideation (1-5)

- 1: Wish to be Dead
- 2: Non-specific Active Suicidal Thoughts
- 3: Active Suicidal Ideation with Any Methods (Not Plan) without Intent to Act
- 4: Active Suicidal Ideation with Some Intent to Act, without Specific Plan
- 5: Active Suicidal Ideation with Specific Plan and Intent

Suicidal Behavior (6-10)

- 6: Preparatory Acts or Behavior
- 7: Aborted Attempt
- 8: Interrupted Attempt
- 9: Actual Attempt (non-fatal)
- 10: Completed Suicide

If no events qualify for a score of 1 to 10, a score of 0 will be assigned (0 = “no event that can be assessed on the basis of C-SSRS”). Higher scores indicate greater severity.

The summaries of the C-SSRS outcomes will be based on the Full analysis set for subjects who have at least 1 post-baseline C-SSRS measurement and a pre-treatment C-SSRS assessment.

A frequency distribution at each scheduled time point will be provided. Shifts from the Baseline value (described in Section 2.2) to the most severe/maximum score during each phase will be summarized.

The maximum score assigned for each subject will also be summarized into one of three broad categories: No suicidal ideation or behavior (0), Suicidal ideation (1 - 5), Suicidal behavior (6 - 10). Shifts from the Baseline value (described in Section 2.2) to the maximum category during each phase will be summarized.

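### The closest-visit rule in SAP 2.3 is applied to a Since Last Visit C-SSRS, so the by-visit suicidality table can show 0 for a window in which an event was recorded

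*SAP*

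**What the plan says.** SAP 2.3 assigns actual visits to protocol visits with one rule for every parameter in Table 1: "If a subject has 2 or more scheduled or unscheduled visits in one visit window, the visit closest to the target day will be used". Ties are settled by recency: "If 2 actual visits are equidistant from the target day within a visit window, the later visit is used". Once assigned to a window, a visit is used up: "it will no longer be used for a later time point except for the end point".

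The C-SSRS is one of the Table 1 parameters and has no exception. After Week 4 of the optimization/maintenance phase its windows run "16 + i*14 to 29 + i*14" days, with target day 22 + 14i.

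Protocol 9.2 fixes the form of the scale: "The C-SSRS assessments in this study will use the Since Last Visit version".

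SAP 6.6.1 plans two kinds of C-SSRS summary. One is by visit: "A frequency distribution at each scheduled time point will be provided". The other is by phase: shifts from baseline to the maximum score, and to the maximum of three categories.

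Both documents foresee more than the scheduled records. When a session is postponed within its visit window, Protocol 9.2 says "all time points (including predose) of the following assessments must be repeated on the actual intranasal treatment session day", and the list that follows includes the C-SSRS. The COVID-19 Appendix (Data Collection) has remote C-SSRS assessments entered as unscheduled if they were done on a day other than the visit day.

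**The concern.** Choosing the reading nearest the target day suits a point measure such as body weight, where either reading describes the subject at about that time. A Since Last Visit scale works differently. Its records cover successive, separate intervals, and a later record does not look back past the one before it. If two C-SSRS records fall in one window, the rule drops one of them, and its interval is then represented nowhere in the by-visit table.

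Effects on suicidal ideation and behaviour are part of the primary objective, and the protocol's C-SSRS endpoint is change over time. The by-visit frequency distribution is the planned C-SSRS summary that shows the time course. A reader will take a 0 in it to mean that nothing was recorded in that period. Under the rule as written, that need not be so.

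**Working it through.** The plan gives no figure to reproduce: there is no hypothesis and no sample size calculation. The check applies the SAP 2.3 rule to the C-SSRS windows.

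**Inputs**
- Windows and targets: SAP Table 1, C-SSRS rows.
- Selection and tie rules: SAP 2.3.
- Permitted timing in optimization/maintenance: "Visit window: ±3 days" (Time and Events Schedule, footnote a). In induction it is ±1 day after Day 1.
- Assumption: each C-SSRS looks back to the previous C-SSRS record, scheduled or not.

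**Windows**
- i = 1, Week 6: Days 16 + 14 = 30 to 29 + 14 = 43; target 22 + 14 = 36.
- i = 2, Week 8: Days 16 + 28 = 44 to 29 + 28 = 57; target 22 + 28 = 50.

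The windows are contiguous, so an extra record shares a window with the scheduled visit whenever that visit took place there.

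**Unscheduled record.** Scores are 0 on Day 36, 9 (actual attempt) on Day 41 and 0 on Day 50.
- Week 6: |36 − 36| = 0 and |41 − 36| = 5, so Day 36 is kept and the row shows 0.
- Week 8: Day 50 is kept. It looks back only to Day 41, so the row shows 0.
- The score of 9 appears in neither row. If Day 50 is the last record of the phase, End Point is also 0.

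With the scheduled visit exactly on Day 36, an unscheduled record on any of the other 13 days of the window is dropped. If the scheduled visit may fall on any of Days 33 to 39, there are 7 × 13 = 91 day combinations. The unscheduled record is kept in 0 of them for a visit on target, and in 1, 3 and 5 for visits 1, 2 and 3 days late. For visits 1, 2 and 3 days early it is kept in 2, 4 and 6, because ties go to the later record. That totals 21, so the unscheduled record is dropped in 70 of 91 and the scheduled one in 21.

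**Repeat after a postponed session.** Both records lie in the same window, so one is always dropped.
- Optimization/maintenance, ±3 days: 21 day pairs. Three are ties, which drop the earlier record. The other 18 split 9 and 9. The original is dropped in 9 + 3 = 12 and the repeat in 9.
- Induction, Day 8, ±1 day: 3 pairs. The original is dropped in 2 and the repeat in 1.
- Example: score 4 on Day 35, repeat score 0 on Day 37. Both are 1 day from target, the tie keeps Day 37, and the row shows 0.

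These counts give every day combination equal weight. They show how the rule behaves and do not estimate how often it matters.

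**Early withdrawal.** With the last visit on Day 36 and the withdrawal visit on any of Days 37 to 43, the Week 6 row keeps Day 36 in all 7 cases. End Point takes the withdrawal record in all 7.

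**Phase maximum**

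| Case | Over all records | Over window-selected records and End Point |
|---|---|---|
| Unscheduled (0, 9, 0) | 9 | 0 |
| Repeat (4, then 0) | 4 | 0 |
| Withdrawal (0, then 9 on Day 41) | 9 | 9 |

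SAP 6.4 says that the ECG maxima use scheduled and unscheduled visits. SAP 6.6.1 has no such sentence for the C-SSRS.

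**The case against.** The best answer is that SAP 2.3 only labels rows. It chooses which record stands for a protocol visit and does not say that other records leave the phase-level summaries. Read plainly, the maximum score in a phase covers every assessment in it, so the Day 41 score of 9 would appear in both shift tables. The contrast with the ECG section is an argument from silence. There is also a second route that uses no windows: SAP 6.1 summarises events potentially related to suicidality as adverse events of special interest, by onset date, and lists deaths and other serious events. An actual attempt belongs there. All of this stands, and it limits the point to the by-visit table. It does not make that table correct.

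Four stronger readings may tempt a reader, and the documents do not support them.
- **Events found at withdrawal vanish.** SAP 2.2 makes the last postbaseline assessment the End Point, 2.3 allows a visit to be reused for it, and Table 1 gives the C-SSRS a labelled End Point row in both phases.
- **Baseline has the same flaw.** Induction Day 1 has no visit window within which to postpone, so this could reach mainly subjects entering optimization/maintenance directly. Exclusion criterion 2 bars ideation items 4 and 5 and any suicidal behaviour since the prior study, which leaves at most levels 1 to 3.
- **The loss favours the drug.** The study has one arm and no hypothesis. The rule can drop either record, and the documents do not show that subjects with extra assessments are more often suicidal.
- **Every repeat loses information.** Protocol 9.2 does not say whether the abandoned session counts as the last visit. If it does not, the repeat covers the whole interval, and dropping the original then need not lose the event.

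**Conclusion.** The point holds in a limited form. Applied as written to a Since Last Visit C-SSRS, the closest-visit rule can put a 0 in a by-visit row although ideation or behaviour was recorded in that window. This rests on a second C-SSRS record falling in the window and on each record looking back only to the one before. The documents foresee repeat and unscheduled records but give no rate, so the number of affected windows is unknown and the worked cases are illustrations.

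The loss is confined to the by-visit frequency distribution, provided the phase maxima are programmed on all records. That is the natural reading of SAP 6.6.1, but it is not stated. The change is still worth making: the rule misreports a planned summary of a primary-objective measure, and correcting it is cheap.

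**What to change.** In SAP 2.3, except the C-SSRS from the closest-visit rule. For each window, report the worst score over all scheduled and unscheduled assessments in it. In SAP 6.6.1, state that the phase maximum score and maximum category use every scheduled, unscheduled and early-withdrawal assessment. SAP 6.1 already takes the most severe occurrence for adverse events, so this follows the plan's own practice.

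With the change, the Week 6 row shows 9 in the unscheduled example and 4 in the repeat example.

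The cost is two or three sentences and a small programming change, with no new data. By-visit frequencies may be slightly higher, and a window with more assessments has more chances to show an event. A table footnote giving the number of assessments per window would let the reader judge this.
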